Anti-diarrhea medications may be introduced if symptoms occur. Previous trials have shown that the diarrhea could be managed with loperamide. The recommended dose of loperamide is 4 mg at first onset, followed by 2 mg every 2 to 4 hours until diarrhea-free for 12 hours.

Table 6.7: General instructions for management of lower gastrointestinal toxicity:

- Monitor all patients for signs and symptoms of enterocolitis (i.e. diarrhea, abdominal pain, blood or mucus in stool with or without fever) and bowel perforation (i.e. peritoneal signs and ileus)
- For diarrhea G1 and G2:
 - oral fluids, loperamide, avoid high fibre/lactose diet
- For diarrhea G2 (> 7 days) or higher, please consider per local institutional guidelines:
 - Blood tests (e.g. hematology and general chemistry including liver function tests (AST, ALT, Bilirubin))
 - Stool (e.g. culture, Clostridium difficile, cytomegalovirus (CMV) or other viral etiology, ova and parasite)
 - GI consultation and Imaging (e.g., CT scan of abdomen and pelvis and GI endoscopy with biopsy)
 - Administer corticosteroids (initial dose of 1-2 mg/kg prednisone or equivalent) followed by taper upon AE improving to ≤ G1 and continue to taper over at least 4 weeks
- For severe and life-threatening diarrhea and/or immune-related colitis:
 - Consider hospitalization or outpatient facility for patients with dehydration or electrolyte imbalance
 - Fluid and electrolytes should be administered via i.v. infusion.
 - Urgent GI consultation and Imaging (e.g., CT scan of abdomen and pelvis and GI endoscopy with biopsy)
 - i.v. corticosteroid should be initiated first followed by oral steroid. Other immunosuppressive treatment should be initiated if irAEs cannot be controlled by corticosteroids

Event	Regorafenib	Pembrolizumab
Diarrhea G1; <4 stools/day over baseline	No modifications	No modifications
Diarrhea G2; 4-6 stools/day over baseline	No modifications, BUT if diarrhea G2 persistent (not back to ≤ G1 in 7 days), hold regorafenib until back to ≤ G1. Restart at same dose level or reduce 1 dose level ^a (at the investigator's discretion).	No modifications, BUT if diarrhea G2 persistent (not back to ≤ G1 in 7 days), withhold until back to ≤ G1; Restart at same dose if resolution to ≤ G1 or baseline ≤ 12 weeks of last infusion and corticosteroid has been tapered,

Diarrhea G3; ≥ 7 stools/day over baseline	G3: Hold regorafenib until back to \leq G1. Restart at same dose level or reduce 1 dose level ^a (at the investigator's discretion)	G3: Withhold; restart at same dose if resolution to \leq G1 or baseline ≤ 12 weeks of last infusion and corticosteroid has been tapered Recurrent G3: permanently discontinue
Diarrhea G4; Life-threatening consequences	G4: Interrupt until \leq G1. Restart at one dose level below ^a	G4: Permanently discontinue

AE= adverse event; ALT= alanine aminotransferase; AST= aspartate aminotransferase; CMV= cytomegalovirus; CT= computed tomography; G1/2/3/4= grade 1/2/3/4; GI= gastrointestinal; i.v.= intravenous(ly); irAE= immune-related adverse event.

a: If reduction required resulting in a dose of less than 80mg q.o.d of regorafenib, then regorafenib will be permanently discontinued.

Prevention/management strategies for rash

All patients should be instructed to use moisturizing lotions. Use of topical steroids for management of rash is recommended. The steroid of choice is triamcinolone, except for head and neck rash which should be managed with hydrocortisone.

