We propose to combine regorafenib and PD1 (pembrolizumab) in colorectal cancer patients in 3rd and 4th line setting. Using a phase I/II design, we will first enroll 3-18 patient on phase I to find the recommended dose for phase II. We will then accrue patients to the phase II portion of the trial with the primary efficacy endpoint of PFS. An extensive biomarker analysis, liquid biopsies and tumor tissue, is planned to identify the population who would most benefit from this combination.

Four patients on dose level 1: 80mg were reviewed by the Phase I DLT Committee. One patient was deemed inevaluable for DLT and was replaced. Three patients were evaluable with no DLT. The trial was recommended to proceed to accrue three patients to dose level 2: 120mg. All three patients at this dose level had either grade 2 or grade 3 rash which required a dose reduction at either cycle 2 or 3. It was determined that the dose level 2: 120mg would

be challenging due to its overall tolerability; therefore, dose level 1: 80mg was recommended to expand and enroll additional three patients for a total of 6 patients to be reviewed.

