6.3.1 Dose Modification Levels

The starting dose of regorafenib is the RD. Study medication will be administered on a 2 weeks on/1 week off schedule [2 weeks out of every 3].

Doses will be delayed or reduced for clinically significant hematologic and non-hematologic toxicities that are related to protocol therapy according to the guidelines shown in the Dose Delays/Dose Modifications table that follows. Dose modifications will follow predefined dose levels. Dose adjustments for hematologic toxicity are based on the blood counts obtained in preparation for the day of treatment.

The modifications of regorafenib will follow the following predefined dose levels:		
Dose level 2	120 mg po qd	Three 40-mg tablets of regorafenib
Dose level 1	80 mg po qd	Two 40-mg tablets of regorafenib

q.d. = *quaque die* (once daily); *q.o.d.* = *quaque altere die* (every other day)

If a subject experiences more than one toxicity, dose reduction should be according to the toxicity with the highest grade

In the case of two or more toxicities of the same grade, the investigator may dose reduce according to that deemed most causally related to study treatment. For Grade 3 toxicity it is acceptable to re-challenge with same dose level at discretion of investigator if toxicity resolved to baseline or lesser grade with medical management within 7 days.

For second occurrence of the same Grade 3 toxicity dose can be reduced to 80mg q.o.d or permanently discontinue at discretion of treating investigator and the rest of the study treatment may be continued. If a dose reduction has been performed, intra-subject dose re-escalation can be considered at the discretion of the treating physician provided that the toxicity(ies) has resolved to baseline.

Tables 6-1, 6-3, and 6-4 outline dose adjustments for toxicities related to regorafenib. Dose adjustment for liver function abnormalities is discussed in table 6-5.

Table 6-1: Recommended dose modification for toxicities except hand-foot-skin reaction, hypertension and ALT/AST/bilirubin			
NCI-CTCAE v5.0^a	Dose Interruption	Dose Modification^b	Dose for Subsequent Cycles
Grade 0-2	Treat on time	No change	No change
Grade 3	Delay until \leq Grade 2 ^c	Reduce by 1 dose level	If toxicity remains < Grade 2, dose re-escalation can be considered at the discretion of the treating investigator. If dose is re-escalated and toxicity (\geq Grade 3) recurs, institute permanent dose reduction.

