Grade 2	1 st occurrence	Consider decreasing dose by one dose level and immediately institute supportive measures. If no improvement, interrupt therapy for a minimum of 7 days, until toxicity resolves to Grade 0-1 ^{b, c}
	No improvement within 7 days or 2 nd occurrence	Interrupt therapy until toxicity resolves to Grade 0-1. ^c When resuming treatment, treat at reduced dose level ^b If dose reduced from the 1 st occurrence then discontinue therapy.
	3 rd occurrence	Discontinue therapy
	4 th occurrence	Discontinue therapy
Grade 3	1 st occurrence	Institute supportive measures immediately. Interrupt therapy for a minimum of 7 days until toxicity resolves to Grade 0-1. ^c When resuming treatment, decrease dose by one dose level. ^{b, d}
	2 nd occurrence	Discontinue therapy
	3 rd occurrence	Discontinue treatment permanently.

a. More conservative management is allowed if judged medically appropriate by the investigator.
 
b. If toxicity returns to Grade 0-1 after dose reduction, dose re-escalation is permitted at the discretion of the investigator if subject has completed one cycle at reduced dose without recurrence of event.
 
c. If there is no recovery after a 4-week delay, treatment with regorafenib will be discontinued permanently.
 
d. Subjects requiring > 1 dose reductions should go off protocol therapy.
 
e. The maximum daily dose is 80 mg. If reduction required resulting in a dose of less than 80mg qod of regorafenib, then regorafenib will be permanently discontinued.
		

Specific guidance for skin and subcutaneous disorders other than HFSR (includes rash, rash erythematous, rash follicular, rash generalized, rash macular, rash maculopapular, rash papular, rash pruritic, exfoliative rash, pruritus, eczema, dermatitis)		
Event	Regorafenib	Pembrolizumab
G2	
 No modifications 	
 Consider withholding for persistent symptoms Restart at same dose if resolution to ≤ G1 or baseline ≤ 12 weeks of last infusion Consider discontinuation if NO resolution ≤ 12 weeks of last infusion ¹

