G3	
 • Hold until recovery to \leq G2 and restart at same dose level or reduce 1 dose level ^a (at the investigator's discretion) • 1st + 2nd re-appearance: Hold until recovery to \leq G2 and reduce 1 dose level ^a (at the investigator's discretion) • 3rd re-appearance: Discontinue 	
 • Hold and restart at same dose if resolution to \leq G1 or baseline \leq 12 weeks of last infusion • Hold and discontinue if NO resolution \leq 12 weeks of last infusion ^b
G4 (when applicable)	
 • Hold until recovery to \leq G2 and reduce 1 dose level ^a • 1st re-appearance: Discontinue 	
 • Discontinue ^b

¹ If toxicity returns to Grade 0-1 after dose reduction, dose re-escalation is permitted at the discretion of the investigator if subject has completed one cycle at reduced dose without recurrence of event.

a: If reductions are required resulting in a dose of less than 80 mg q.o.d. of regorafenib, then regorafenib will be permanently discontinued. For grade 3, patient could stay on regorafenib for the first appearance, or hold until resolved to grade 2 or less, restart at the same dose level or lower after discussion between investigator and study chair.

b: after consultation with study chair, if toxicity considered at least possibly related to pembrolizumab.

If reduction required resulting in a dose of less than 80mg qod of regorafenib, then regorafenib will be permanently discontinued.

(For studies with combination therapy, consider including the following statement "The other study treatment may be continued").

At first occurrence of HFSR, independent of grade, prompt institution of supportive measures such as topical emollients, low potency steroids, or urea-containing creams should be administered.

Recommended prevention/management strategies for skin toxicities consistent with HFSR are summarized below:

Control of calluses

Before initiating treatment with regorafenib:

- Check condition of hands and feet.
- Suggest a manicure/pedicure, when indicated.
- Recommend pumice stone use for callus or 'rough spot' removal.

During regorafenib treatment:

- Avoid pressure points.
- Avoid items that rub, pinch or create friction.

Use of creams

- Non-urea based creams may be applied liberally.

- Keratolytic creams (e.g. urea-based creams, salicylic acid 6%) may be used sparingly and only to affected (hyperkeratotic) areas.

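### Section 6.3.1 and its tables contradict each other on reducing, re-challenging and stopping regorafenib, and if 80 mg is the recommended dose the level list shows no step below it

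*Combined protocol and SAP*

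**What the plan says.** Section 6.3.1 sets the starting point and the ladder. "The starting dose of regorafenib is the RD", and "The modifications of regorafenib will follow the following predefined dose levels": level 2 is 120 mg once daily and level 1 is 80 mg once daily. Section 6.1 lists the same two. The abbreviation for every-other-day dosing is explained under the list, but no alternate-day level is in it.

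The general text below the list gives two Grade 3 rules. First, "it is acceptable to re-challenge with same dose level at discretion of investigator", provided the toxicity has resolved to baseline or a lesser grade with medical management within 7 days. Second, "For second occurrence of the same Grade 3 toxicity dose can be reduced to 80mg q.o.d or permanently discontinue at discretion of treating investigator". The same sentence lets the rest of study treatment continue.

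The tables that follow (6-1 general, 6.3 hand-foot-skin reaction, the unnumbered table for other skin disorders, 6-4 hypertension, 6.5 liver, 6.7 diarrhea) each order or offer a one-level reduction. Footnote d of Table 6.3 states "Subjects requiring > 1 dose reductions should go off protocol therapy", and footnote c of Table 6-4 says the same for hypertension. Footnote e of Table 6.3 adds "The maximum daily dose is 80 mg".

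On which dose goes forward, Section 1.1 reports that 120 mg was judged challenging for tolerability and that "dose level 1: 80mg was recommended to expand and enroll additional three patients", to make six for review.

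**The concern.** An investigator with a patient on 80 mg daily who has a Grade 3 toxicity has to combine the level list, the general text, a toxicity table and its footnotes. These do not give one answer. Depending on which is followed, regorafenib could be restarted at the same dose, moved to alternate days, or stopped, and pembrolizumab could continue or stop with it.

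This is first a safety matter, because the same event could be managed differently between patients or sites. Section 3 foresees one or two further institutions. It also touches a phase II objective. Section 7.2 defines tolerability as the median duration of combination therapy, and Section 4 judges it against a value at least 20% better than 1.7 months (1.7 × 1.2 = 2.04, given there as 2.0). A choice between reducing and stopping regorafenib changes how long a patient is on the combination.

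**Working it through.** The plan gives no figure to reproduce, so the check sets the rules side by side.

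**Step 1: which dose is the starting point.** Section 1.1 expands 80 mg after 120 mg proved hard to tolerate, and footnote e of Table 6.3 caps the daily dose at 80 mg. Both point to 80 mg as the recommended dose. Neither declares it. The next steps take 80 mg as an assumption.

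**Step 2: listed steps below it.** Levels listed: 2 (120 mg, 80 mg). Levels below 80 mg daily: 0. If the alternate-day floor is read as an unlisted level: 1. If 120 mg were the recommended dose, there would be 1 listed level below it, and a first reduction would have a destination.

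**Step 3: what each source says about regorafenib at Grade 3 or its nearest equivalent row.**

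| Source | First event | Recurrence | Alternate-day floor in notes |
|---|---|---|---|
| General text | Same dose allowed if resolved within 7 days | 80 mg alternate days, or stop | Named as an option, not as a level |
| Table 6-1 | Delay, then one level lower | No rule except after re-escalation | No |
| Table 6.3 (hand-foot-skin) | Interrupt, then one level lower | Discontinue | Yes |
| Other skin disorders | Same dose or one level lower | One level lower at 1st and 2nd re-appearance, at discretion; stop at 3rd | Yes |
| Table 6-4 (hypertension) | Hold, same dose; one level lower if uncontrolled | Discontinue if it recurs despite reduction and treatment | Yes |
| Table 6.5 (ALT/AST up to 8 × ULN; bilirubin above 3 mg/dL) | Hold, then one level lower | Discontinue at 1st re-appearance | Yes |
| Table 6.7 (diarrhea) | Hold, same dose or one level lower | No regorafenib rule | Yes |

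So 6 of 6 tables use a one-level step, 5 of 6 carry the floor, and Table 6-1 does not.

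**Step 4: direct conflicts.**
- *First Grade 3 event.* The text allows the same dose, on a condition. Table 6-1 reduces and does not mention that condition.
- *Second Grade 3 event.* The text offers alternate-day dosing or stopping. Tables 6.3 and 6.5 allow only stopping. No sentence says which prevails.
- *What stopping means.* Suppose alternate-day 80 mg counts as one step. A second reduction from 80 mg daily is then both more than one reduction and below the floor. Footnote d of Table 6.3 takes that patient off protocol therapy, while footnote e discontinues regorafenib only. Footnote c of Table 6-4 holds the same pair of rules. The general text lets the rest of treatment continue. A template note left in after the skin table only suggests considering such a sentence.
- *Cap and list.* Footnote e caps the daily dose at 80 mg, while 120 mg remains a listed level.

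**The case against.** The strongest reply is that the protocol already handles the step below 80 mg. A floor at alternate-day 80 mg makes sense only if that dose can be reached, and five of the six tables state it. That largely stands: the intended step can be guessed. But it is never called a dose level, the text attaches it to a second Grade 3 event only, and Table 6-1, the default for general toxicities, omits it.

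A second reply is that re-challenge is a conditional exception to tables headed as recommended or suggested, and that Section 6.3.1 refers readers to those tables. This reading is possible for the first event. It does not settle the second, where the text offers an option that Tables 6.3 and 6.5 withhold and no order of precedence is given.

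Four stronger readings are tempting, and the documents do not support them:
- *Different numbers of reductions by toxicity are an error.* They may be deliberate, since each toxicity has its own table.
- *The Grade 3 row for other skin disorders cannot be carried out from 80 mg.* The row starts "1st + 2nd re-appearance: Hold until recovery to" Grade 2 or better, and each reduction is at the investigator's discretion, so it permits 0 to 3. Its footnote a says what happens below the floor.
- *Ambiguous decisions fall close to the tolerability threshold.* The rash-driven reductions at cycle 2 or 3 in Section 1.1 occurred at 120 mg, where a lower level is listed. For 80 mg that section reports three evaluable patients without DLT and no frequency or timing of reductions.
- *Re-escalation breaches the 80 mg cap.* Returning from alternate days to 80 mg daily would respect it.

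**Conclusion.** The contradictions are real and lie in the text. On the assumption that 80 mg is the recommended dose, 0 levels are listed below it while six tables use a one-level reduction. Treating the floor as a level gives one implied step.

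The other conflicts do not need that assumption: re-challenge against reduction at the first Grade 3 event, alternate-day dosing against discontinuation at the second, regorafenib alone against all protocol therapy, and the 80 mg cap against the 120 mg row.

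The consequence is inconsistent handling of the same event, with a possible effect on duration of combination therapy. How large, or in which direction, cannot be worked out from the documents, because they give no rate of qualifying events at 80 mg. No sample size, power or error rate changes. The point should be fixed, but it is a matter of reconciling wording and does not show that the tolerability endpoint is compromised.

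**What to change.** Reconcile Section 6.3.1 with its tables and footnotes:
1. Make the level list show every level that a reduction can reach from the phase II starting dose, so that each one-level reduction has a defined destination or a stated stop.
2. State whether the general Grade 3 text or the toxicity-specific table takes precedence, and align that text with Table 6-1.
3. Reconcile footnote e of Table 6.3 with the 120 mg row.
4. State consistently, in the text and in the footnotes to Tables 6.3 and 6-4, whether stopping regorafenib ends all protocol therapy, and resolve the leftover template note.

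Limits on reductions may differ by toxicity if each is stated explicitly. The sponsor and the investigator decide the doses and rules; none is proposed here. The cost is a wording amendment, with the usual ethics review and the agreement that Section 13.1 requires. Design and analysis stay as they are.

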- Alpha hydroxyl acids (AHA) based creams may be applied liberally 2 times a day. Approximately 5% to 8% provides gentle chemical exfoliation.
- Topical analgesics (e.g. lidocaine 2%) are to be considered for pain control.
- Topical corticosteroids like clobetasol 0.05% should be considered for subjects with Grade 2 or 3 HFSR. Avoid systemic steroids.

Tender areas should be protected as follows:

- Use socks/gloves to cover moisturizing creams
- Wear well-padded footwear
- Use insole cushions or inserts (e.g. silicon, gel)
- Foot soaks with tepid water and Epson salts

Hypertension

Hypertension is a known AE associated with regorafenib treatment. Subject will have their blood pressure measured at least weekly at the study site during the first 6 weeks of treatment. If additional blood pressure measurements are done outside the study site, and the blood pressure is > 140 mm Hg systolic or > 90 mm Hg diastolic (NCI CTCAE v5.0), then the subject must contact study personnel. The management of hypertension, including the choice of antihypertensive medication, will be performed according to local standards and to the usual practice of the investigator. Every effort should be made to control blood pressure by medical means other than study drug dose modification. If necessary, Table 6-4 outlines suggested dose reductions.

Table 6-4: Management of Treatment-Emergent Hypertension

Grade (CTCAE v5.0)	Antihypertensive Therapy	Regorafenib Dosing
1 Prehypertension (systolic BP 120 - 139 mmHg or diastolic BP 80 - 89 mmHg)	None	
 Continue regorafenib Consider increasing blood pressure (BP) monitoring
2 Systolic BP 140 - 159 mmHg or diastolic BP 90 - 99 mmHg, OR Symptomatic increase by > 20 mmHg (diastolic) if previously within normal limits	Treat with the aim to achieve diastolic BP ≤ 90 mm Hg: If BP previously within normal limits, start anti-hypertensive monotherapy If patient already on anti-hypertensive medication, titrate up the dose.	
 Continue regorafenib If symptomatic, hold regorafenib until symptoms resolve AND diastolic BP ≤ 90 mm Hg^a. When regorafenib is restarted, continue at the same dose level.

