3 Systolic BP ≥ 160 mmHg or diastolic BP ≥ 100 mmHg OR More than one drug or more intensive therapy than previously used indicated	Treat with the aim to achieve diastolic BP ≤ 90 mm Hg: Start anti-hypertensive medication AND/OR Increase current anti-hypertensive medication AND/OR Add additional anti-hypertensive medications.	
 Hold regorafenib until diastolic BP ≤ 90 mm Hg, and if symptomatic, until symptoms resolve.^a When regorafenib is restarted, continue at the same dose level. If BP is not controlled with the addition of new or more intensive therapy, reduce by 1 dose level.^b If Grade 3 hypertension recurs despite dose reduction and antihypertensive therapy, discontinue therapy
4 Life-threatening consequences (eg, malignant hypertension, transient or permanent neurologic deficit, hypertensive crisis)	Per institutional guidelines	Discontinue therapy

a. Patients requiring a delay of >4 weeks should go off protocol therapy
 
b. If BP remains controlled for at least one cycle, dose re-escalation permitted per investigator's discretion.
 
c. Patients requiring >1 dose reductions should go off protocol therapy. If reduction required resulting in a dose of less than 80mg q.o.d of regorafenib, then regorafenib will be permanently discontinued.
		

Liver Function Abnormalities

For patients with observed worsening of serum liver tests considered related to regorafenib (i.e. where no alternative cause is evident, such as post-hepatic cholestasis or disease progression), the dose modification and monitoring advice in Table 6-5 should be followed.

Regorafenib is a UGT1A1 inhibitor. Mild, indirect (unconjugated) hyperbilirubinemia may occur in patients with Gilbert's syndrome.

Table 6.5: Dose Modification/interruption for LIVER toxicity

General instructions:

If any of below outlined events will occur: Monitor liver function tests weekly or more frequently until recovery to baseline or stabilization.

If reduction required resulting in a dose of less than 80mg qod of regorafenib, then regorafenib will be permanently discontinued.

For any G3/4 increases in ALT/AST or bilirubin:

If the increases are primarily seen under ongoing regorafenib treatment (e.g. last pembrolizumab infusion was given one week before):

Closely monitor for potential de-challenge, i.e. whether a decrease in ALT/AST and/or bilirubin values is seen within 3 days of regorafenib interruption.

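### Table 6-4 holds regorafenib for Grade 3 hypertension on systolic or diastolic pressure, but its release criterion contains no systolic value

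*Combined protocol and SAP*

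**What the plan says.** Protocol section 6.3.1, under Hypertension, manages treatment-emergent hypertension through Table 6-4. The Grade 3 row has these parts:

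- **Entry.** Systolic pressure of at least "160 mmHg or diastolic BP" of at least 100 mmHg. Needing more than one drug, or more intensive therapy than before, also counts.
- **Treatment.** "Treat with the aim to achieve diastolic BP" of 90 mm Hg or lower, by starting, increasing or adding antihypertensives.
- **Hold and release.** "Hold regorafenib until diastolic BP" is 90 mm Hg or lower and, in a symptomatic patient, until symptoms resolve.
- **Restart dose.** "When regorafenib is restarted, continue at the same dose level".
- **Exception on dose.** "If BP is not controlled with the addition of new or more intensive therapy, reduce by 1 dose level".
- **Limits.** Grade 3 that recurs despite dose reduction and therapy means discontinuation. A delay of more than 4 weeks takes the patient off protocol therapy (footnote a).

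The Grade 2 row is built the same way. It is entered on systolic 140–159 or diastolic 90–99 mmHg, and a symptomatic patient is held until symptoms resolve and diastolic pressure is 90 mm Hg or lower.

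The text above the table leaves management to local standards and the investigator's usual practice. It asks that pressure be controlled by medical means before the dose is changed, and says "If necessary, Table 6-4 outlines suggested dose reductions".

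**The concern.** A hold should end when the condition that started it has resolved. Here either pressure can start the hold, but only one of them is looked at when it ends. A patient who is Grade 3 purely by systolic pressure is told to stop regorafenib and, by the same row, has already satisfied the pressure condition for taking it again at the same dose.

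What is at stake is individual safety. Section 6.3.1 names hypertension as a known adverse event of regorafenib, and a site following the row literally could resume the drug while the patient is still Grade 3. No efficacy endpoint, sample size or error rate is involved.

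**Working it through.** The documents give no figure to reproduce. The check sets the entry rule of the Grade 3 row against its release rule. The blood pressures are illustrations, not data from the documents.

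**Entry against resolution, Grade 3 row**

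| Element | Systolic value | Diastolic value |
|---|---|---|
| Entry | ≥160 mmHg | ≥100 mmHg |
| Treatment aim | none | ≤90 mm Hg |
| Hold release | none | ≤90 mm Hg |

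Systolic pressure is in the trigger but in 0 of the 2 resolution criteria. Diastolic pressure must fall at least 100 − 90 = 10 mmHg below its Grade 3 threshold. Systolic pressure need not fall at all.

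**Worked cases, asymptomatic patient**

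1. *178/86.* Grade 3, because 178 ≥ 160 (178 − 160 = 18 mmHg above the threshold). The release condition is already met, because 86 ≤ 90. The hold lasts 0 days.
2. *170/105, falling to 165/88.* Grade 3 on both pressures at entry. At 165/88 the release condition is met (88 ≤ 90), but systolic pressure is still 165 − 160 = 5 mmHg above the threshold. The row permits restart. The bullet on uncontrolled pressure may make that restart one level lower.
3. *165/105, falling to 135/85.* Diastolic is 90 or lower and systolic is below 160. The rule works as intended.

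The rule fails when systolic pressure is the limb that stays high, and only then.

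**Symptomatic Grade 2.** At 155/85 with symptoms, the diastolic part of the release is already met (85 ≤ 90). The hold therefore ends on symptoms alone, whatever the systolic reading.

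**Is the omission likely to be deliberate?** Other Grade 3 holds of regorafenib end on recovery of the toxicity that caused them: Table 6-1 at Grade 2 or lower, hand-foot skin reaction at Grade 0–1, other skin events at Grade 2 or lower, ALT/AST at Grade 2 or lower or baseline, and diarrhea at Grade 1 or lower. The protocol uses systolic pressure in exclusion criterion 3, in the rule on readings taken outside the site (above 140 systolic or 90 diastolic) and in the grade definitions. It gives no reason for dropping it at restart.

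**Scale.** Section 1.4.2 reports Grade 3 or higher hypertension in 7% of the regorafenib group of CORRECT. If that rate applied to the 69 phase II patients in the synopsis, 0.07 × 69 = 4.8, or about 5, would reach this row. That is an assumption: CORRECT used 160 mg for three weeks in four, against 80 or 120 mg for two weeks in three here. The share with systolic-only elevation is not given, so under this assumption the number affected runs from 0 to about 5.

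**The case against.** The best defence is that the row does not stand alone. The bullet on uncontrolled pressure refers to blood pressure, not diastolic pressure, and 165 mmHg on added therapy is hard to call controlled. Case 2 would then lead to a one-level reduction. Grade 4 hypertension means discontinuation, so extreme pressures are covered. Antihypertensives must still be started or increased, the table's reductions are described as suggestions, local standards apply, and pressure is checked weekly for the first 6 weeks.

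All of this lowers the risk, and it is why the point is minor. None of it supplies the missing value. The bullet sets the dose at restart, not the time of restart. It leaves control undefined in a row whose only numeric target is diastolic. Weekly checks give readings without a threshold to compare them with. Section 13.1 asks for strict adherence to the protocol's specifications, so a site could fairly follow the row as written.

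A reader might infer something stronger: that Table 6-4 contradicts the general text of 6.3.1, which finds it acceptable after Grade 3 toxicity to "re-challenge with same dose level at discretion of investigator if toxicity resolved to baseline or lesser grade with medical management within 7 days". The documents do not support that. The sentence is a discretionary permission and does not forbid a same-dose restart in other circumstances. The same text hands over to the tables ("Tables 6-1, 6-3, and 6-4 outline dose adjustments for toxicities related to regorafenib"), and the title of Table 6-1 excludes hypertension, so Table 6-4 is naturally read as governing. Nor do the 7 days in that sentence conflict with the 4 weeks in Table 6-4. The first is a condition on one permission. The second is the longest delay before treatment stops, and Tables 6-1 and 6-3 have the same 4-week limit.

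It would also be too strong to say that release rests on diastolic pressure alone, since symptoms must resolve in symptomatic patients.

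**Conclusion.** The gap is real and narrow. Followed literally, the Grade 3 row gives no working release criterion for isolated systolic hypertension: the hold lasts 0 days at 178/86, and restart is permitted at 165/88 with the patient still Grade 3 by systolic pressure. The symptomatic Grade 2 hold has the same omission.

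The finding rests on a literal reading of one table and would stand even if the general Grade 3 text were not there. It does not show a conflict between parts of 6.3.1, and it does not show that any patient would be left unmanaged. How many would be affected cannot be derived from the documents. It is a minor patient-safety correction with no effect on PFS, power or error rates.

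**What to change.** In the next amendment:

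1. **Grade 3 release.** Continue the hold until systolic pressure is below 160 mm Hg and diastolic pressure is 90 mm Hg or lower and, in symptomatic patients, until symptoms have gone. Below 160 is the table's own Grade 3 boundary and the least that makes the rule coherent. The clinical team may choose a stricter value, for example 140 mm Hg or lower. That figure is the systolic partner of 90 in the rule on readings taken outside the site, although there it prompts a call to study personnel and is not a restart threshold.
2. **Treatment aim and control.** Use the same pair for the Grade 3 treatment aim and to define control in the dose-reduction bullet.
3. **Symptomatic Grade 2.** Add a systolic value suited to that grade to the release. A limit of 160 would do nothing there, because Grade 2 is already below it.
4. **Optional.** Add one sentence saying that Table 6-4 governs hypertension.

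The cost is a small edit to one table. The downside is slightly longer holds in a few patients, some of whom could reach the 4-week limit if a strict systolic value is chosen.
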